Revised Protocol 01	28-Oct-2020	The primary reasons for these changes are to align dose modification criteria [REDACTED] with the current Common Terminology Criteria for Adverse Event (CTCAE) version (v5); add serologic testing for severe acute respiratory syndrome coronavirus 2 (SARS-CoV-2) status; and incorporate additional updates to improve alignment across protocol sections and/or clarify expectations for eligibility, assessments, sample collections, treatment administration, and country-specific requirements.
Original Protocol	29-May-2020	Not applicable

OVERALL RATIONALE FOR PROTOCOL AMENDMENT 04:

[figure not shown]
[figure not shown]
The primary rationale for Protocol Amendment 04 is to make overall study design changes and clarify several items throughout the protocol.

[figure not shown]
The original design of CA224-073 was a 3-arm study randomized 2:1:2 with the following treatment arms:

- Arm A: nivolumab 480 mg every 4 weeks (Q4W)
- Arm B: nivolumab 480 mg Q4W + relatlimab 480 mg Q4W
- Arm C: nivolumab 480 mg + relatlimab 960 mg Q4W

24 participants were randomized in Arm C.

[figure not shown]
SUMMARY OF KEY CHANGES FOR PROTOCOL AMENDMENT 04		
Section Number & Title	Description of Change	Brief Rationale
Title page	Changed Medical Monitor from [REDACTED], to [REDACTED], Clinical Scientist from [REDACTED] to [REDACTED], and their associated contact information.	To report important personnel changes.
Table 2-1: Screening Procedural Outline (CA224073)	Removed the following text from notes corresponding to the “Pre-screening for Tumor Tissue Sample” row: “All other procedures may be performed within 14 days if pre-screening ICF is used.”	To avoid confusion regarding procedures that can be done with pre-screening informed consent form (ICF).
	Modified the language from “Most” to “All” inclusion/exclusion criteria in notes corresponding to the Inclusion/Exclusion Criteria row.	For clarity.

SUMMARY OF KEY CHANGES FOR PROTOCOL AMENDMENT 04		
Section Number & Title	Description of Change	Brief Rationale
	Added the following text to notes corresponding to the row Physical Examination: “Full physical examination including height, weight, and BMI. Any findings during the PE will be recorded as medical history in the participant’s medical records and on the appropriate CRF.”	Clarified requirements for physical examination.
	Oxygen saturation was added to vital sign assessments.	Clarified requirements for vital sign assessments.

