Abbreviations: AE = adverse event; BICR = Blinded Independent Central Review; DCR = disease control rate; DOR = duration of response; HCC = hepatocellular carcinoma; IO = immuno-oncology; ORR = objective response rate; OS = overall survival; PFS = progression-free survival; RECIST = Response Evaluation Criteria in Solid Tumors; SAE = serious adverse event; TKI = tyrosine kinase inhibitor.

Overall Design:

This Phase 2 study will evaluate the safety and efficacy of relatlimab in combination with nivolumab in participants with 2L or 3L IO-naive HCC.

[figure not shown]
As of 19-July-2021, participants are being randomized 1:1 to receive:

[figure not shown]
- Arm A:** Nivolumab 480 mg Q4W
- Arm B:** Nivolumab 480 mg Q4W+ Relatlimab **480** mg Q4W

- [REDACTED]

Arm C: Nivolumab 480 mg Q4W+ Relatlimab **960** mg Q4W

[REDACTED] 24 participants were randomized to Arm C.

For Protocol Amendment 03, all participants in Arm B and Arm C were re-consented. All new participants at the time had signed the updated informed consent for Protocol Amendment 03.

This is an open-label, randomized Phase 2 study in adult (≥ 18 years) male and female participants with advanced, Child-Pugh A, IO-naive HCC who have experienced progression that was demonstrated radiographically on or after one or two prior TKI therapies in the advanced/metastatic setting. Participants must not be amenable for management with surgery or locoregional therapy or have progressed after surgery or locoregional therapy.

Stratification will occur by region (Asia [excluding Japan] vs Rest of the World [including Japan]) and macrovascular invasion and/or extrahepatic spread (MVI/EHS; present or absent). For the purposes of randomization, LAG-3 will also be treated as a stratification factor.

MVI is defined as:

- Hepatic vein tumor thrombus, OR
- Inferior vena cava tumor thrombus, OR

- Portal vein tumor thrombus; Vp3/Vp4 (presence of a tumor thrombus in the main trunk of the portal vein or a portal vein branch contralateral to the primarily involved lobe or first-order branches of the portal vein) participants are also eligible.

EHS is defined as presence of metastatic disease in lymph nodes or distant sites outside the liver.

[figure not shown]

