5.4.4 Rationale for Stratification Factors

Stratification will occur by:

- Region (Asia [excluding Japan] vs rest of the world [including Japan])
- MVI/EHS (yes or no)
- LAG-3 expression 

Recent pivotal studies in this indication and line/setting of therapy used the following stratification factors: the CA209040 study that led to the approval in 2L stratified by HCC HCV vs non-HCV and presence of Investigator-assessed vascular invasion (VI) or EHS vs absence of VI/EHS; while the KEYNOTE-240 study, which did not meet its endpoints with pembrolizumab monotherapy

approval, stratified by geographic region (Asia excluding Japan, vs non-Asia including Japan), MVI (yes or no) and AFP (< 200 ng/mL vs > 200 ng/mL).

A number of randomized Phase 3 trials in HCC that followed the sorafenib pivotal trials have failed to demonstrate positive outcomes. These include 4 Phase 3 trials in the 1L setting with sunitinib, brivanib, linifanib, and erlotinib.^{53, 54, 55, 56} The reasons for trial failure are considered heterogeneous and include lack of understanding of critical drivers of tumor progression/dissemination, liver toxicity, flaws in trial design, or marginal antitumor potency.⁵⁷ With respect to trial design, publications have cited potential imbalances in prognostic baseline factors.

[figure not shown]
The randomized Phase 3 trials were mostly stratified by the presence or absence of VI and/or EHS, geographic region, and Eastern Cooperative Oncology Group (ECOG) performance status. Despite stratification and randomization, notable differences were observed in the outcomes. Subset analysis of the 2 pivotal sorafenib trials showed differences in the outcomes of participants who had VI/EHS compared to those who did not have VI/EHS. Participants who had VI/EHS had worse outcomes than participants without VI/EHS.^{58, 59} This study will therefore stratify by VI/EHS.

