The impact of differing HCC patient populations and different approaches to clinical practice in the different regions is still important to consider. Based on pivotal trial results, differences in outcome are also captured in outcome by infectious vs non-infectious etiology. Based on World Health Organization (WHO) data, the prevalence of HCV is highest in the eastern Mediterranean region (>2%),⁶⁰ and HBV prevalence is 2-7% in Mediterranean countries, Japan, central Asia, the Middle East, and parts of South America.⁶¹ These regions where HBV and HCV infection and consequent HCC is prevalent are in the Asian region. The Japanese HCC population is different from the other non-Japanese Asian HCC populations, with a higher prevalence of HCV-HCC and a better screening system. The KEYNOTE-224 and IMbrave 150 studies stratified by region, including Japan to the rest of the world.⁶² Therefore, this study will not stratify by etiology, assuming the majority of HCC with infectious origin comes from the Asian countries. This study will therefore stratify by region.

[figure not shown]
[REDACTED]

[REDACTED] To balance the expression across arms, LAG-3 will also be treated as a stratification factor.

[REDACTED]

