10.3.1 Efficacy Analyses

Efficacy Analyses are described in [Table 10.3.1-1](#) and will be performed on the randomized population. If Arm C is closed or dropped and number of participants randomized in Arm C is small, the primary efficacy comparison will be performed between Arm B vs Arm A and the efficacy analysis in Arm C will be descriptive.

Table 10.3.1-1: Efficacy Analyses

Endpoint	Statistical Analysis Methods
Primary	The difference in ORR between relatlimab in combination with nivolumab (Arm B) vs nivolumab (Arm A) will be presented by BICR using RECIST v1.1 computed using a simple proportion and 95% Clopper-Pearson confidence interval for this study. In addition, posterior probability of the true difference of ORR assessed by BICR using RECIST v1.1 to fall in the activity interval given the data will be provided. Also, the posterior mean of the difference of ORR between the two arms and the corresponding 90% credible intervals will also be provided. The efficacy analysis in Arm C will be descriptive.
Secondary	ORR assessed by Investigator and DCR will be computed and analyzed using frequency statistics. DOR, PFS, and OS will be analyzed using the Kaplan-Meier method.

Abbreviations: BICR = Blinded Independent Central Review; DCR = disease control rate; DOR = duration of response; LAG-3 = lymphocyte activation gene 3; OS = overall survival; PFS = progression-free survival; ORR = objective response rate; RECIST = Response Evaluation Criteria in Solid Tumors.

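### The primary ORR comparison, as visible, is a crude difference that ignores the randomization strata and the change in A:B allocation from 2:1 to 1:1

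*Combined protocol and SAP*

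**What the plan says.** For the primary endpoint, Table 10.3.1-1 in Section 10.3.1 says "The difference in ORR between relatlimab in combination with nivolumab (Arm B) vs nivolumab (Arm A) will be presented by BICR", by RECIST v1.1. The method it gives for this is "computed using a simple proportion and 95% Clopper-Pearson confidence interval for this study". It adds a posterior probability for the true difference, a posterior mean difference and a 90% credible interval. Section 10.3.1 places the efficacy analyses on all randomized participants, so the periods before and after the allocation change are pooled.

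On allocation, the rationale for Protocol Amendment 04 records: "The original design of CA224-073 was a 3-arm study randomized 2:1:2 with the following treatment arms". Arms A, B and C are nivolumab alone, nivolumab with relatlimab 480 mg, and nivolumab with relatlimab 960 mg. It also states that "24 participants were randomized in Arm C". The Synopsis (Overall Design) then says: "As of 19-July-2021, participants are being randomized 1:1 to receive" Arm A or Arm B.

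On stratification, the Synopsis says "Stratification will occur by region (Asia [excluding Japan] vs Rest of the World [including Japan]) and macrovascular invasion and/or extrahepatic spread", with LAG-3 as a third factor. Section 5.4.4 gives the reasons. For vascular invasion and spread: "Participants who had VI/EHS had worse outcomes than participants without VI/EHS". Region is linked to outcome through etiology. For LAG-3 the visible reason is balance: "To balance the expression across arms, LAG-3 will also be treated as a stratification factor".

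Section 10.3 describes its text as a summary and leaves detail to a SAP to be finalized before database lock. No separate SAP text is in the document supplied, and parts of Section 10 are redacted.

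**The concern.** There are two separate issues.

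**Allocation period.** Both arms recruited under both ratios, but Arm A has a larger share of early participants than Arm B. When data are pooled across a change of ratio, any ORR difference between periods passes in part into the treatment difference. If later participants respond more often, the crude estimate favors Arm B; if they respond less often, it favors Arm A. This follows from the design and is not a chance imbalance. A shift between periods is plausible: Section 6.1 shows that Amendment 02 (15 April 2021) replaced the requirement for progression on sorafenib or lenvatinib with one or two lines of any TKI.

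**Stratification factors.** Leaving out the factors used to randomize does not bias the comparison within one allocation ratio. It makes the interval slightly conservative and loses a little precision.

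The study is open label to the sponsor (Section 7.3). An adjustment chosen late could look data-driven, which is a reason to name it in advance.

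**Working it through.** **Inputs from the document.** Original A:B:C ratio 2:1:2 and Arm C = 24 (Amendment 04 rationale); 1:1 from 19 July 2021 (Synopsis); 226 in Arms A and B (Section 5.2); nivolumab ORR 14% (Synopsis), used here for both arms under no treatment effect. The stated totals agree: 226 + 24 = 250, and 250/0.70 = 357 enrolled. No power calculation for ORR is visible to reproduce.

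**1. Implied counts** (derived; per-arm counts by period are not given).
- Early: A = 24, B = 12.
- Late: (226 − 36)/2 = 95 per arm.
- Totals: A = 119, B = 107.

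**2. Early share.** 24/119 = 20.2% and 12/107 = 11.2%, a gap of 9.0 points. With early counts of 20–28 in A and 8–16 in B, the gap runs from 20/115 − 16/111 = 3.0 points to 28/123 − 8/103 = 15.0 points.

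**3. Bias of the crude difference** = (share in B − share in A) × (early ORR − late ORR) = −0.0895 × period difference.
- 10-point period difference: 0.9 points in size (0.3–1.5 over the counts above).
- 20-point period difference: 1.8 points.

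**4. Standard errors at 14%.**
- Crude: √[0.14 × 0.86 × (1/119 + 1/107)] = 4.62 points, so the biases are 0.9/4.62 = 0.19 SE and 1.79/4.62 = 0.39 SE.
- Mantel-Haenszel by period: weights 24×12/36 = 8 and 95×95/190 = 47.5, so SE = √(0.1204/55.5) = 4.66 points.
- 1:1 period only: √(0.1204 × 2/95) = 5.03 points.

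**5. Effect on a test.** At an assumed two-sided 5% level, with late ORR 14% and early ORR higher, type I error becomes 5.4% for a 10-point period difference and 6.5% for a 20-point one.

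**6. Simulation check** (400,000 trials, no treatment effect). With ORR 6% early and 16% late, the crude mean is +0.9 points and the period-stratified mean is 0.0. With 22% early and 12% late, the crude mean is −0.9.

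**7. Precision from the strata.** Take 8 equal strata with additive gaps of g per factor around 14%. The share of variance explained is 3(g/2)²/0.1204, which is 0.25% for g = 2 points and 4.0% for g = 8. A normal-approximation half-width of 1.96 × 4.623 = 9.06 points becomes 9.06 × √0.9975 = 9.05 or 9.06 × √0.960 = 8.88. Once a period term is also fitted, this gain is about nil at this sample size.

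**8. A model with all four terms.** Standardized logistic regression with main effects for region, MVI/EHS, LAG-3 and period removed the bias in simulation, with SE 4.64–4.70 points against 4.57–4.63 for the crude difference. The period term cannot be estimated if none of the 36 early participants responds. That has probability 0.94^36 = 11% if early ORR is 6%, and 0.86^36 = 0.4% if it is 14%.

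**The case against.** The strongest reply is that the effect is too small to matter in a study that Section 5.1.4.1 calls exploratory. A 20-point period shift exceeds the whole 14% reference ORR, and even then the bias is 0.39 SE. This stands, and it limits how much weight the point can carry.

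No period difference has been shown either. Amendment 02 came about three months before the ratio changed, so allocation period is an imperfect proxy for eligibility. Section 3.2 reports nivolumab activity regardless of etiology and prior sorafenib. The VI/EHS evidence in Section 5.4.4 comes from sorafenib trials and is not specific to ORR. All of this stands: the shift is plausible, not demonstrated.

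The early counts are inferred. Section 7.2 lets an over-enrolled arm close temporarily, so the actual counts may depart from the ratio. The 3.0 to 15.0 point range covers moderate departures only.

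Clopper-Pearson is a method for a single proportion, so the sentence in the table may describe per-arm rates and leave the method for the difference unstated. That ambiguity is real, but on either reading no adjustment is specified.

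The SAP or redacted text may hold an adjusted analysis. That cannot be excluded, so the point concerns the visible text only.

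Finally, about 32 responders (14% of 226) is few for a model with five terms. Simulation answers most of this: convergence is a problem mainly when early ORR is very low, and a fallback named in advance covers that case.

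**Conclusion.** The point holds for the visible text. The stated primary comparison is crude, uses none of the three randomization factors, and pools across a change in A:B allocation that links period to arm. The bias is about 0.09 times any ORR difference between periods: 0.9 points for a 10-point difference and 1.8 points for a 20-point one, against a standard error near 4.6 points. These sizes rest on early counts inferred from the 2:1:2 ratio and Arm C = 24, on a 14% reference ORR, and on a period shift that is assumed. Omitting the strata alone is a minor matter of precision. The reason to change is protection from period bias at negligible cost. This should be done, but it does not threaten the study's conclusions unless the period shift is large.

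**What to change.** In the protocol or SAP:

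- Name the primary estimator as the ORR difference from standardized logistic regression, with main effects for the IRT values of region, MVI/EHS and LAG-3 and for allocation period (2:1 or 1:1). State the interval method for that difference, and keep Clopper-Pearson for the per-arm rates.
- Do not cross period with the 8 strata. About 12 early Arm B participants over 8 cells average 12/8 = 1.5 each, and with equal cells at least one would be empty in about 91% of draws.
- Prespecify the fallback: if the model does not converge, use a Mantel-Haenszel risk difference stratified by period alone.
- Put the same terms in the Bayesian model behind the posterior probability, posterior mean and 90% credible interval.
- Report the crude difference as supportive, and the 1:1-period difference (about 95 vs 95, SE 5.03 points) as a sensitivity analysis.
- Report the actual per-arm counts by period.

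The cost is wording and routine programming, since the factors and randomization dates are already in IRT. The statistical cost is an SE of 4.66 against 4.62 points for period stratification, and about the same for the full model. If the SAP already contains an equivalent adjustment, a cross-reference in Table 10.3.1-1 is enough.

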10.3.2 Safety Analyses

All safety analyses described in Table 10.3.2-1 will be performed on the treated population.

[figure not shown]
Table 10.3.2-1: Safety Analyses

Endpoint	Statistical Analysis Methods
Primary	Not applicable.
Secondary	Incidence of AEs, SAEs, AEs leading to discontinuation, death, and laboratory abnormalities will be analyzed using frequency statistics.

Abbreviations: AE = adverse event; IMAE = immune-mediated adverse event; SAE = serious adverse event.

[figure not shown]
[figure not shown]

[figure not shown]

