	Added the following text to notes corresponding to the row 12-lead ECG: “ECGs must be collected and assessed using the site’s own ECG machine.”	To maintain consistency with the text stated in future visits.
	Replaced “24 hours” with “1 day” in the notes corresponding to the row, Pregnancy Test (WOCBP only).	To update window to 1 day instead of 24 hours and maintain consistency among sections.
Section 5.1.1: Screening Period	Added the following text: If the subject is awaiting central laboratory results, then the participant does not have to re consent until day 42 (additional +14 days beyond screening window). Other screening procedures should be conducted within the windows specified in Table 2-1 .	For clarity.
Table 2-2: On-Treatment Assessments (CA224073)	
 • Clarified on-treatment monitoring requirements between Arm A and B. • [REDACTED] • [REDACTED] • Added: Assessments of PR and CR must be confirmed at least 4 weeks (28 days) after initial response. 	
To clarify that the enhanced monitoring requirements are specific to Arm B.
 
[REDACTED]
 
To clarify confirmatory imaging requirements.

SUMMARY OF KEY CHANGES FOR PROTOCOL AMENDMENT 04		
Section Number & Title	Description of Change	Brief Rationale
	
 Replaced “24 hours” with “1 day” in the notes corresponding to the row, Pregnancy Test (WOCBP only). Added the following text to notes corresponding to the row Body Imaging: " disease progression (unless treatment beyond progression) or treatment discontinuation (including treatment beyond progression), whichever occurs later." 	
To maintain consistency among sections.
 
To clarify imaging requirements and maintain consistency across protocol.

Table 2-3: Follow-up Procedural Outline (CA224073)	
Added the following text to notes corresponding to the row Targeted Physical Examination: “Any findings during the PE will be evaluated for AEs and reported as such.”
	
To emphasize adverse event (AE) reporting requirements during follow-up.

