^a Some of the assessments referred to in this section may not be captured as data in the CRF. They are intended to be used as safety monitoring by the treating physician. Additional testing or assessments may be performed as clinically necessary or where required by institutional or local regulations.

Table 2-2: On-Treatment Assessments (CA224073)

Procedure ^a	Cycle 1 (4 weeks)		Cycle 2+ (4 weeks)		End of Treatment (EOT) ^b	Notes ^c (All windows are based on calendar days.)
	D1	D15 (± 3 days)	D1 (± 3 days)	D15 (± 3 days)		
Eligibility Assessments						
Inclusion/Exclusion Criteria	X					Cycle 1 Day 1 only: All inclusion/exclusion criteria should be confirmed prior to first dose.
Safety Assessments						
Targeted Physical Examination	X	X	X	X	X	To be performed only as clinically indicated prior to dosing, using local oncology/hepatology physical examination guidelines when new symptoms or laboratory abnormalities occur.
Child-Pugh Score	X		X		X	See Appendix 5 .
Vital Signs	X	X	X	X	X	Including BP, heart rate, and temperature prior to dosing. BP and heart rate should be measured after the participant has been seated quietly for at least 5 minutes.
Oxygen Saturation	X		X		X	Prior to dosing; collect at rest via pulse oximetry. Oxygen levels will be used in combination with clinical signs and symptoms and radiographic images to evaluate pulmonary/respiratory status. Changes in O2 levels will not be used in isolation to document or diagnose pulmonary toxicity.
Physical Measurements and Performance Status	X		X		X	Weight and ECOG (see Appendix 6), prior to dosing.
Adverse Event and Serious Adverse Event Assessments	Continuously					All AEs (SAEs or non-serious AEs), including those associated with SARS-CoV-2 infection, must be collected continuously during the treatment period. See Section 9.2 . AEs are graded per CTCAE v5, except as described for hepatic and endocrinopathies [REDACTED].
Concomitant Medication Use	Continuously					

Table 2-2: On-Treatment Assessments (CA224073)

Procedure ^a	Cycle 1 (4 weeks)		Cycle 2+ (4 weeks)		End of Treatment (EOT) ^b	Notes ^c (All windows are based on calendar days.)
	D1	D15 (± 3 days)	D1 (± 3 days)	D15 (± 3 days)		
Coagulation Profile	X	X	X	X	X	Including PT/INR and aPTT. See Section 9.4.4 .
Disease Assessment: Serum Alpha-fetoprotein	X		X		X	See Section 9.4.4 .

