12-lead ECG	X	X	X			12-lead ECGs should be recorded after the participant has been supine for at least 5 minutes. ECGs must be collected and assessed predose on Day 1 of each cycle using the site's own ECG machine; done on Day 1 only starting with Cycle 2.
2D Echocardiogram	See notes.					For all participants: performed locally as clinically indicated.
Chest Radiograph	See notes.					As clinically indicated.
Pregnancy Test (WOCBP only)	X		X			Serum or urine (minimum sensitivity equivalent units 25 IU/L or equivalent units of HCG) within 1 day prior to administration of first dose of study treatment and then every 4 weeks (± 7 days), regardless of dosing schedule. An extension up to 72 hours prior to the start of study treatment is permissible in situations where results cannot be obtained within the standard 24-hour window.
Efficacy Assessments						
Body Imaging	See notes.					Contrast-enhanced CT of the chest, CT or MRI of abdomen and pelvis (including required tri-phasic CT or MRI of the liver), and all other known and/or suspected sites of disease should occur

Table 2-2: On-Treatment Assessments (CA224073)

Procedure ^a	Cycle 1 (4 weeks)		Cycle 2+ (4 weeks)		End of Treatment (EOT) ^b	Notes ^c (All windows are based on calendar days.)
	D1	D15 (± 3 days)	D1 (± 3 days)	D15 (± 3 days)		
						every 8 weeks starting from randomization (± 7 days). Imaging should continue as per schedule until disease progression (unless treatment beyond progression) or treatment discontinuation (including treatment beyond progression), whichever occurs later. Assessments of PR and CR must be confirmed at least 4 weeks (28 days) after initial response. See Section 9.1.1 for further details.
Brain Imaging					See notes.	Participants with a history of brain metastasis or symptoms should have a surveillance MRI study per standard of care (approximately every 12 weeks from randomization), or sooner if clinically indicated. CT of the brain without and with contrast can be performed if MRI is contraindicated. See Section 9.1.1 for further details.
Other Imaging: Bone Scan					See notes.	See Section 9.1.1 ; as clinically indicated per local standards.

Table 2-2: On-Treatment Assessments (CA224073)

Procedure ^a	Cycle 1 (4 weeks)		Cycle 2+ (4 weeks)		End of Treatment (EOT) ^b	Notes ^c (All windows are based on calendar days.)
	D1	D15 (± 3 days)	D1 (± 3 days)	D15 (± 3 days)		
Additional Research Sampling	See notes.				See Section 9.8.4.	

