- ^c Some of the assessments referred to in this section may not be captured as data in the CRF. They are intended to be used as safety monitoring by the treating physician. Additional testing or assessments may be performed as clinically necessary or where required by institutional or local regulations.

Table 2-3: Follow-up Procedural Outline (CA224073)

Procedure	Safety Follow-up Visit 1 and 2 ^a	Survival Follow-up visits ^b	Notes ^c
Safety Assessments			
Targeted Physical Examination	X		Targeted physical examination to be performed only as clinically indicated. Any findings during the PE will be evaluated for AEs and reported as such.
Vital Signs	X		Weight, BP, heart rate, and temperature.
Assessment of Signs and Symptoms	X		
Adverse Event and Serious Adverse Event Assessments	X	See notes.	All SAEs and non-serious AEs should be collected continuously during the treatment period and for a minimum of 135 days following discontinuation of study treatment. Participants will be followed for all SAEs, non-serious AEs of special interest (as defined in Section 9.2), and all AEs (SAEs and non-serious AEs) associated with confirmed or suspected SARS-CoV-2 infection until resolution, the condition stabilizes, the event is otherwise explained, the event is deemed irreversible, the participant is lost to follow-up (as defined in Section 8.3), or for suspected cases, until SARS-CoV-2 infection is ruled out.
Review of Concomitant Medications	X		See Section 7.7 .
Performance Status	X		ECOG performance status Score (see Appendix 6).
Laboratory Tests	X (see notes)		For Follow-up Visit 1, onsite/local including hematology, serum chemistry, and urinalysis, as outlined in Section 9.4.4 . Repeat at Follow-up Visit 2 only if study treatment-related toxicity persists.
Pregnancy Test (WOCBP only)	X		Serum or urine. Pregnancy testing is only required at Follow-up Visits 1 and 2, unless increased frequency and duration is required per local regulations.
Coagulation Profile	X		Including PT/INR and aPTT.

Table 2-3: Follow-up Procedural Outline (CA224073)

Procedure	Safety Follow-up Visit 1 and 2 ^a	Survival Follow-up visits ^b	Notes ^c
[REDACTED]			
[REDACTED]			
Efficacy Assessments			

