4 OBJECTIVES AND ENDPOINTS

Objectives and endpoints are presented in Table 4-1.

Table 4-1: Objectives and Endpoints

Objective	Endpoint
Primary	

 To evaluate the efficacy of relatlimab in combination with nivolumab relative to nivolumab monotherapy in IO therapy-naive participants after prior treatment with TKI therapy 	
 ORR assessed by BICR using RECIST v1.1
Key Secondary	

 To investigate safety and tolerability of relatlimab in combination with nivolumab in participants with advanced HCC 	
 Incidence of AEs, SAEs, and AEs leading to discontinuation, deaths, and clinical laboratory test abnormalities

 To further evaluate the preliminary efficacy of relatlimab in combination with nivolumab 	
 DCR, DOR, and PFS assessed by BICR per RECIST v1.1 ORR, DCR, DOR, and PFS assessed by Investigator per RECIST v1.1 OS

Table 4-1: Objectives and Endpoints

Objective	Endpoint

Abbreviations: AE = adverse event; BICR = Blinded Independent Central Review; [redacted]
DCR = disease control rate; DOR = duration of response; [redacted]
[redacted] HCC = hepatocellular carcinoma;
[redacted] IO = immuno-oncology; [redacted]
[redacted] ORR = objective response rate; OS = overall
survival; PFS = progression-free survival; [redacted]
[redacted] RECIST = Response Evaluation Criteria in Solid Tumors; SAE = serious adverse event; [redacted]
[redacted] TKI = tyrosine kinase inhibitor.

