9.2.6 Laboratory Test Result Abnormalities

[figure not shown]
The following laboratory test result abnormalities should be captured on the non-serious AE CRF page or SAE Report Form electronic, as appropriate. Paper forms are only intended as a back-up option when the electronic system is not functioning.

- Any laboratory test result that is clinically significant or meets the definition of an SAE
- Any laboratory test result abnormality that required the participant to have study treatment discontinued or interrupted
- Any laboratory test result abnormality that required the participant to receive specific corrective therapy

It is expected that wherever possible, the clinical rather than laboratory term would be used by the reporting Investigator (eg, anemia vs low hemoglobin value).

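### Arm-B-specific enhanced monitoring may account for part of any Arm B excess in asymptomatic laboratory abnormalities and related AEs, because the safety tables do not separate assessments common to both arms from Arm-B-only ones

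*Combined protocol and SAP*

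**What the plan says.** Section 10.3.2 (Table 10.3.2-1) sets the safety analysis in one line: "Incidence of AEs, SAEs, AEs leading to discontinuation, death, and laboratory abnormalities will be analyzed using frequency statistics". It applies to the treated population. The visible text names no between-arm test and draws no distinction by the kind of assessment that produced a finding.

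The Table 2-2 entry in the summary of key changes for Amendment 04 records the change as "Clarified on-treatment monitoring requirements between Arm A and B" and the reason as "To clarify that the enhanced monitoring requirements are specific to Arm B". That line explains the schedule now in force.

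The rows of Table 2-2 that can be read do not differ by arm. The echocardiogram, for example, is "For all participants: performed locally as clinically indicated", and on AE collection the table says: "All AEs (SAEs or non-serious AEs), including those associated with SARS-CoV-2 infection, must be collected continuously during the treatment period". The on-treatment laboratory and thyroid rows do not appear in the public text, and neighbouring entries are blacked out.

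Section 9.2.6 lists the laboratory results that go onto the AE or SAE form, among them "Any laboratory test result that is clinically significant or meets the definition of an SAE". Section 9.2.8 does the same for significant worsening on an ECG, x-ray or any other safety assessment.

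The safety objective in Section 4 is "To investigate safety and tolerability of relatlimab in combination with nivolumab in participants with advanced HCC". The research hypothesis in Section 3.1.1 is a favourable benefit/risk profile relative to nivolumab alone. Section 7.3 makes the trial open label to sponsor and site, and Section 10.3 leaves the SAP to be finalized before database lock.

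**The concern.** Randomization makes the arms comparable at baseline. It does not protect against unequal ascertainment built into the visit schedule. If Arm B has assessments that Arm A does not, a silent abnormality that is equally common in both arms can be recorded more often in Arm B. A crude frequency table then shows an excess that cannot be told apart from toxicity of relatlimab.

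The endpoints most exposed are asymptomatic laboratory abnormalities and the low-grade AEs recorded because of them. Some may carry further: under Sections 7.4.2 and 8.1.1 a laboratory abnormality can lead to a dose delay or to discontinuation, and under Section 9.2.7 potential drug-induced liver injury meeting the defined criteria is reported as an SAE. Whether liver tests differ by arm cannot be seen.

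At stake is the safety half of the benefit/risk judgement. The distortion would run against the combination, and blinding does not offset it.

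**Working it through.** **1. Is there a route from unequal monitoring to unequal counts?**

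- Monitoring differs by arm: stated in the Amendment 04 summary, Table 2-2 entry.
- Test findings become counted events: Sections 9.2.6 and 9.2.8.
- Counts are summarized as they stand: Table 10.3.2-1.
- Arm A and Arm B rates will be read side by side: not stated in the safety section, but hard to avoid given the hypothesis in Section 3.1.1.

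The first three links are in the text. The fourth is an inference about how descriptive tables will be used.

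**2. How large could it be?** The documents give no AE or laboratory rate and no detection rate, so there is no figure of the plan's to reproduce. What follows is an illustration.

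Inputs:
- Arms A and B together: approximately 226 (Section 5.2). Taken here as 226 / 2 = 113 per arm, an assumption, because allocation was 2:1:2 before it became 1:1.
- True incidence T, the same in both arms: 10%, 20%, 40% (assumed).
- Probability that an occurring event is detected and recorded, sA and sB: pairs shown below (assumed).

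Formulas: observed rate = T × s; spurious difference = T × (sB − sA); ratio = sB / sA.

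| sA / sB | T = 10%: A vs B (diff.) | T = 20% | T = 40% | Ratio |
|---|---|---|---|---|
| 1.00 / 1.00 | 10 vs 10 (0) | 20 vs 20 (0) | 40 vs 40 (0) | 1.00 |
| 0.90 / 1.00 | 9 vs 10 (1) | 18 vs 20 (2) | 36 vs 40 (4) | 1.11 |
| 0.80 / 0.95 | 8 vs 9.5 (1.5) | 16 vs 19 (3) | 32 vs 38 (6) | 1.19 |
| 0.80 / 1.00 | 8 vs 10 (2) | 16 vs 20 (4) | 32 vs 40 (8) | 1.25 |
| 0.60 / 0.90 | 6 vs 9 (3) | 12 vs 18 (6) | 24 vs 36 (12) | 1.50 |

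Example: 0.40 × (0.90 − 0.60) = 0.12, or 12 points.

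**3. Would such an excess look real?** With 113 per arm and a two-sided 5% comparison of proportions, the chance of a nominal result showing more events in Arm B is 2.5% with equal detection. For T from 10% to 40% it becomes 4–9% for 0.90/1.00, 6–15% for 0.80/0.95, 8–24% for 0.80/1.00 and 13–50% for 0.60/0.90. A 119/107 split gives nearly the same values. The plan names no such test; the figures only show how easily a reader could be misled by confidence limits or by eye.

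**4. Which endpoints?** Detection of a death does not depend on the assessment schedule, so sA = sB and the difference is zero. The rows with unequal detection are most plausible for silent laboratory findings, and less so for SAEs and AEs leading to discontinuation.

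**The case against.** The case against has real force.

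- The premise rests on one rationale line. The extra monitoring could be a laboratory test, an observation period or a visit, and no readable row of Table 2-2 differs by arm. This stands as a limit on size and on which endpoints are touched. It does not remove the sponsor's own statement that the schedules differ.
- A footnote to Table 2-2 says that some assessments may not be entered in the CRF. Arm-B-only results might then never reach the laboratory tables. That is possible, but a clinically significant result would still be recorded as an AE under Section 9.2.6.
- Table 10.3.2-1 names no between-arm comparison, and the safety objective describes the combination only. This is correct. A reader might infer that the plan formally compares raw counts; it does not say so. The risk lies in how descriptive rates are read against the Section 3.1.1 hypothesis.
- Parts of Section 10.3 are blacked out and the SAP was still to be finalized, so mitigation may exist elsewhere. This also stands: the claim is only that none is visible.

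Three stronger readings are tempting and not supported. One is that part of any Arm B excess must be detection, across every safety endpoint. The documents show a mechanism, not its operation, and deaths are outside it. The second is a much larger effect. If Arm B were always tested and Arm A only 10–40% of the time for a wholly silent event, the excess would be 6–9 points at a true rate of 10% and 12–18 points at 20%, but nothing in the documents supports those testing rates. The third draws on the follow-up laboratory rule in Table 2-3, "Repeat at Follow-up Visit 2 only if study treatment-related toxicity persists". That rule is worded identically for all arms and does not show that Arm B is tested more often.

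**Conclusion.** The point holds as a risk of detection bias that the visible plan does not address. Part of any Arm B excess in asymptomatic laboratory abnormalities, and in AEs arising from them, may reflect more testing. The size is unknown: about 1 to 12 points over the detection pairs tried, zero with equal detection. The upper end needs a 40% true incidence with 60% against 90% detection. All of these rates are assumptions. The conclusion rests on the Amendment 04 rationale describing the schedule in force, and on at least some Arm-B-only assessments yielding results that are recorded.

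**What to change.** Keep the full frequency tables. In Table 10.3.2-1 and the SAP, add:

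1. A between-arm laboratory-abnormality table restricted to tests and visits scheduled in both arms, named as the table to use for reading Arm B against Arm A.
2. A separate Arm B table for results of Arm-B-only assessments, without a comparator column.
3. Where the preferred term or the data allow it, a sensitivity AE table without events that correspond only to Arm-B-only tests.

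Items 1 and 2 need SAP text and table programming only. Item 3 depends on being able to link an AE to the test that found it. No field for that is visible, so it should be conditional. It should also stay a sensitivity table, because it removes real Arm B events that might later have become clinically evident. The downside is small: a few more tables, and some Arm B findings missing from the restricted comparison though still present in the full tables. No study procedure changes.
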